### **5.8.8. Vital Signs**

Vital signs parameters include weight (kg), heart rate, systolic and diastolic blood pressure, respiratory rate, and temperature ( $^{\circ}\text{C}$ ). Vital signs are recorded at Screening and on Days 1 of each cycle and End of Treatment. For each parameter at each time point, the observed values and change from baseline will be summarized. Vital sign data will also be listed for all patients.

### **5.8.9. ECG Results**

12-lead ECG results are recorded at Cycle 1 Day 1 and at the end of treatment visit. The quantitative ECG assessments (Ventricular rate, QRS width, PR interval, and QTcF interval) will be summarized at each time point.

ECG overall interpretation (normal, abnormal/not clinically significant [NCS] and abnormal/clinically significant [CS]) will be presented for actual values and changes from baseline (Screening observation) to each post-baseline visit, expressed as Improvement, No Change, and Deterioration, defined as follow:

- Improvement = CS to Abnormal NCS, Abnormal NCS to Normal
- Deterioration = Normal to Abnormal NCS or CS, Abnormal NCS to Abnormal CS
- No change = Normal to Normal, Abnormal NCS to Abnormal NCS, Abnormal CS to Abnormal CS

If a result is missing for any patient, then an ‘Unknown’ category will be presented. ECG results will be listed for all patients.

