15.2.2. Primary Endpoint Analysis

Safety analysis: To assess clinical safety, AEs, vital sign measurements and clinical laboratory information will be summarized. AEs will be coded using the Medical Dictionary for Regulatory Activities (MedDRA). Changes from baseline for clinical laboratory values and vital signs will be summarized over time. Descriptive statistics and shift tables will be generated as appropriate.

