### 5.8.5. Safety Analyses

The safety endpoints will be summarized based on the Safety Population. The safety endpoints include the incidence of treatment emergent adverse events, changes in laboratory tests, vital signs and ECG's.

Adverse events (AEs) will be coded using MedDRA Version 20.0. Severity of AEs will be coded using National Cancer Institute Common Toxicity Criteria for Adverse Events version 4.0 (NCI-CTCAE v4.0).

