### **5.8.7. Laboratory Evaluations**

Results from the following laboratory parameters, recorded at their respective time points will be summarized by time point:

**Hematology** (Screening, Day 1 of each cycle, End of Treatment, Post Treatment Follow Up and End of Study): RBC, white blood cell (WBC) with differential, hemoglobin, hematocrit, reticulocyte count, platelet count, mean corpuscular volume (MCV), mean corpuscular hemoglobin (MCH), mean corpuscular hemoglobin concentration (MCHC), red blood cell distribution width (RDW), and nucleated RBCs (nRBCs)

**Chemistry** (Screening, Day 1 of Cycle 1 and Day 1 of every other subsequent cycles, End of Treatment and End of Study): Sodium, potassium, aspartate aminotransferase (AST), alanine aminotransferase (ALT), lactate dehydrogenase (LDH), total bilirubin, direct bilirubin, alkaline phosphatase, blood urea nitrogen (BUN)/urea, creatinine, gamma-glutamyl transpeptidase (GGT), calcium, phosphorus, glucose, amylase, lipase, total protein, albumin, and uric acid

**Urine Analysis** (Day 1 of Cycle 1 and every 4 subsequent cycles, End of Treatment and End of Study): pH, specific gravity, protein, glucose, ketones, blood, leukocyte esterase, nitrite, microscopic examination (if performed)

**Urine Chemistry** (Day 1 of Cycle 1 and every 4 subsequent cycles, End of Treatment and End of Study): Microalbumin and creatinine; albumin/creatinine ratio

Categorical and numeric variables will be presented separately. Actual values and changes in hematology and biochemistry laboratory values from baseline will be summarized by time point. Shift tables for the hematology and biochemistry laboratory parameters comparing values above, within and below the normal reference range at baseline to the end of treatment visit will be presented using standard reference ranges.

Peripheral blood smears are taken at Screening, Day 1 of Cycle 1 and every 4 subsequent cycles, and at the end of treatment visit. These data will be listed only.

All laboratory values will be listed for all patients.

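### SAP 5.8.9 plans no change from baseline for ventricular rate, PR, QRS or QTcF, although SAP 5.8.5 makes changes in ECGs a safety endpoint

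*SAP*

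**What the plan says.** SAP 5.8.5 defines the endpoints: "The safety endpoints include the incidence of treatment emergent adverse events, changes in laboratory tests, vital signs and ECG's".

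SAP 5.8.9 sets the ECG visits: "12-lead ECG results are recorded at Cycle 1 Day 1 and at the end of treatment visit". For the continuous measures the whole plan is: "The quantitative ECG assessments (Ventricular rate, QRS width, PR interval, and QTcF interval) will be summarized at each time point". Change is planned only for the overall interpretation (normal, abnormal not clinically significant, abnormal clinically significant), as "changes from baseline (Screening observation) to each post-baseline visit, expressed as Improvement, No Change, and Deterioration". The section ends: "ECG results will be listed for all patients".

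The neighbouring sections go further. For laboratory values, SAP 5.8.7 says: "Actual values and changes in hematology and biochemistry laboratory values from baseline will be summarized by time point". For vital signs, SAP 5.8.8 says: "For each parameter at each time point, the observed values and change from baseline will be summarized".

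SAP 5.1 fixes the baseline. Patients who roll over without interruption keep their A536-03 baseline. Patients with interruption use the last value on or before their first A536-05 dose, falling back on the A536-03 baseline where the A536-05 one is unscheduled or inadequate. SAP 5.2 lists n, mean, SD, median, minimum and maximum as the default summary, and states that everything is descriptive.

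**The concern.** The primary objective is long-term safety, and the SAP defines the ECG endpoint as a change. For the four measures that carry the size of a change, no change is planned. The one ECG change analysis works on a coarse read. If QTcF rose by 50 ms (an illustrative figure) and the reader's category stayed the same, the patient would be counted as unchanged.

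A reader of the report would then have to compare the Cycle 1 Day 1 row with the end-of-treatment row. That comparison gives no measure of how much individual patients changed. It also starts, for rollover patients, from an ECG that is not their baseline, and it need not involve the same patients at both ends.

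**Working it through.** The documents give no ECG figure, sample size calculation or power, so there is nothing to reproduce. The check sets the sections side by side and then works out what two visit rows can and cannot show.

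**1. What is planned for each measure**

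| Measure | SAP section | Values by visit | Change from baseline |
|---|---|---|---|
| Hematology, biochemistry | 5.8.7 | yes | yes |
| Vital signs | 5.8.8 | yes | yes |
| Overall ECG interpretation | 5.8.9 | yes | yes, in three categories |
| Ventricular rate, QRS, PR, QTcF | 5.8.9 | yes | none stated |

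The three categories are not exhaustive either. They cover eight of the nine possible transitions (two improvements, three deteriorations, three unchanged). Clinically significant to normal is in none of them.

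**2. What two visit rows leave undetermined**

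With equal SD s at both visits and within-patient correlation r, the SD of change is s × √(2(1 − r)). The rows give s but not r. Taking s = 20 ms (assumption):

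- r = 0.3: 20 × √1.4 = 23.7 ms
- r = 0.5: 20 × √1.0 = 20.0 ms
- r = 0.7: 20 × √0.6 = 15.5 ms
- r = 0.9: 20 × √0.2 = 8.9 ms

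The same pair of rows fits any of these. So neither the spread of individual change nor a confidence interval for its mean can be read from them. The minimum and maximum in SAP 5.2 are extremes of values, not of changes.

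**3. Which ECG starts the comparison**

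For patients without interruption, A536-05 Cycle 1 Day 1 may take place 28 (± 7) days after the last A536-03 dose and may coincide with the A536-03 end-of-treatment visit (Protocol 9.1). The phase 1 mean half-life was 14.9 to 16.2 days (Protocol 7.3), so 28 days is 28/16.2 = 1.7 to 28/14.9 = 1.9 half-lives. That ECG follows up to 3 months of treatment. Their SAP 5.1 baseline is the A536-03 one, and the A536-03 schedule (SAP Appendix 2) has a Screening ECG. The A536-05 end-of-treatment ECG is itself due 28 (± 7) days after a dose. For these patients the two rows therefore compare two post-exposure ECGs, and a shift already present at Cycle 1 Day 1 would sit in both. The documents do not give the split between patients with and without interruption.

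SAP 4.1 includes A536-03 data for rollover patients, so an A536-03 Screening row may also be shown. Section 5.8.9 does not list it as a time point, and the comparison would still not be paired.

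**4. Who is in each row**

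Let f be the share with a starting ECG but no end-of-treatment ECG, A the starting mean of those with both, and M the starting mean of those missing the second. With no true change:

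- starting row = (1 − f)A + fM
- end row = A
- difference = f(A − M)

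If those missing start higher by the gap shown (assumptions; a gap the other way reverses the sign):

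| f | gap 5 ms | gap 10 ms | gap 15 ms |
|---|---|---|---|
| 0 | 0 | 0 | 0 |
| 0.1 | −0.5 | −1.0 | −1.5 |
| 0.2 | −1.0 | −2.0 | −3.0 |
| 0.4 | −2.0 | −4.0 | −6.0 |

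A 20,000-run simulation with 100 patients, f = 0.4, a 10 ms gap, SD 20 ms, correlation 0.7 and no true change gave −3.98 ms for the difference of rows and 0.02 ms for the paired change.

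**The case against.** **Precision.** A reader might infer that visit summaries make the estimated shift less precise and cost power. The documents do not support that. When the same patients are in both rows, the difference of means is the mean paired change, with the same true standard error. The wider SD × √(2/n) appears only if someone treats the visits as independent. With 60% to 100% attendance and correlations of 0.3 to 0.9, the true standard error of the row difference is 0.94 to 1.61 times the paired one, so it is sometimes smaller. No test is planned, so power is not the yardstick. What is missing is the reported SD and interval of change.

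**Attendance.** A reader might also infer that the ECG result is confounded with who reaches end of treatment. The Protocol asks every treated patient to complete that visit (14.6), at discontinuation for early stoppers (12.3). Death and loss to follow-up are listed withdrawal reasons (9.3), so gaps are plausible, but neither their number nor their direction is given. The effect in step 4 is conditional. Pairing removes only the baseline-composition part, because a paired change is also seen only in attenders.

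**Attribution.** A single-arm study cannot attribute a shift to the drug under either display.

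**No breach, no lost data.** Protocol 15.2.2 commits only to this: "Changes from baseline for clinical laboratory values and vital signs will be summarized over time". The read shift meets the wording of SAP 5.8.5, if coarsely. Protocol 7.4 names no QT or conduction risk. Listings allow pairs to be formed later, and ECG findings judged clinically relevant are recorded as adverse events (Protocol 14.1, 14.5).

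All of this stands, and it limits the point to the planned tables. It does not explain why the ECG measures are treated differently from laboratory values and vital signs. A listing is not a summary, and a change derived afterwards carries less weight than a prespecified one.

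**Conclusion.** The point holds as a gap in the planned displays. For ventricular rate, PR, QRS and QTcF, the SAP gives no estimate of the change that it names as a safety endpoint. Individual shifts within one read category appear only in listings. For patients without interruption, the Cycle 1 Day 1 row is not the baseline that the SAP defines. These three statements rest on the text alone.

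The composition shift of 1 to 3 ms rests on two assumptions, 20% missing and a baseline gap of 5 to 15 ms. It is zero if everyone has an end-of-treatment ECG or if the two groups start alike. No loss of power or precision is claimed, no drug effect on QTcF is implied, and there is no breach of the protocol. It is an improvement available at almost no cost.

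**What to change.** In SAP 5.8.9, add change from baseline to each post-baseline ECG for ventricular rate, PR, QRS and QTcF, in patients with both values: n, mean, SD, median, range and 95% CI.

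State the baseline by reference to SAP 5.1: the A536-03 baseline ECG for patients without interruption, and the last value on or before the first A536-05 dose for patients with interruption. The A536-05 Cycle 1 Day 1 ECG then counts as post-baseline for the first group. Align the Screening label in 5.8.9 with this, because the Study 05 schedule has no separate Screening ECG, only a Cycle 1 Day 1 ECG that may be taken up to 28 days before.

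Report how many patients lack an end-of-treatment ECG, and keep the interpretation shift table. Whether to add categorical QTcF limits is the sponsor's choice and not part of this point.

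Cost: SAP wording and one extra table from data already collected, with no new assessment.

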### **5.8.10. Physical Examination**

A physical examination is conducted at Screening, Cycle 1 Day 1 and Day 1 of every 4 cycles and at the end of treatment and end of study visits. Physical exam details will be listed only.

### **5.8.11. Long-term Follow-up**

A listing of Long-term Follow-up data including the visit date, malignancy status, and survival status will be provided.

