2. SCHEDULE OF EVENTS

	Screening ¹	Cycle 1	Cycle 2	Cycle 3	Cycle 4	Cycle 5	Cycle 6	Cycle 7	Cycle 8	Cycle 9
		C1D1 ²	C2D1 ²	C3D1 ²	C4D1 ²	C5D1 ²	C6D1 ²	C7D1 ²	C8D1 ²	C9D1 ²
Informed consent	X ¹									
Inclusion/Exclusion	X	X ²								
Medical history ³	X									
QoL Questionnaires ⁴		X				X				X
Physical examination	X	X				X				X
Vital signs ⁵	X	X	X	X	X	X	X	X	X	X
ECOG Status	X	X		X		X		X		X
ECG (12 lead) ⁶		X								
Bone marrow aspirate ⁷	X	X ⁷								X ⁷
Serum iron studies ⁸		X				X				X
Erythropoietin levels		X				X				X
Hematology ⁹	X	X	X	X	X	X	X	X	X	X
Peripheral blood smear		X				X				X
Serum chemistry ¹⁰	X	X		X		X		X		X
Urinalysis and Urine Chemistry ¹¹	X	X				X				X
Anti-Drug Antibody ¹²		X				X				X
PK collection		X				X				X
PD biomarkers ¹³		X				X				X
Pregnancy test ¹⁴	X	X	X	X	X	X	X	X	X	X
Evaluate transfusion frequency ¹⁵	X	X	X	X	X	X	X	X	X	X
Administer ACE-536		X	X	X	X	X	X	X	X	X
Concomitant medications and AEs	Collected Continuously									

	Cycle 10	Cycle 11	Cycle 12	Cycle 13	Cycle 14	Cycle 15	Cycles 16 - 87 ^{2,16}	EOT ¹⁷	PTFU ¹⁸	LTFU ¹⁹	EOS ²⁰
	C10D1 ²	C11D1 ²	C12D1 ²	C13D1 ²	C14D1 ²	C15D1 ²					
Informed consent											
Inclusion/Exclusion											
Medical history ³											
QoL Questionnaire ⁴					(X) ⁴			X			
Physical examination					X			X			
Vital signs ⁵	X	X	X	X	X	X		X			
ECOG Status		X		X		X		X			
ECG (12 lead) ⁶								X			
Bone marrow aspirate ⁷					(X) ⁷			X ⁷			
Serum iron studies ⁸					X			X	X		
Erythropoietin levels					X			X	X		
Hematology ⁹	X	X	X	X	X	X		X	X		
Peripheral blood smear					X			X			
Serum chemistry ¹⁰		X		X		X		X			
Urinalysis and Urine Chemistry ¹¹					X			X			
Anti-Drug Antibody ¹²					X			X ¹²			
PK Collection					X			X			
PD biomarkers ¹³					X			X			
Pregnancy test ¹⁴	X	X	X	X	X	X		X			
Evaluate transfusion frequency ¹⁵	X	X	X	X	X	X		X	X		
Administer ACE-536 ²	X	X	X	X	X	X					
Monitoring for AEs of special interest ²¹ (Refer to Section 14.1 for details)	After signing ICF and until at least 3 years post last dose of IP or until death, loss to follow up, withdrawal of consent for further data collection.										
Survival follow-up ²¹										X	X
Concomitant medications and AEs	Collected Continuously										

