- ²¹ Long-Term Post-Treatment Follow-Up for overall survival (OS), progression to AML, other malignancies/pre-malignancies (please refer to [Section 14.1](#) for details) may be conducted by record review (including public records if allowed by local regulations) and/or telephone contact with the patient, family, or the patient's treating physician. The investigator must make every effort to obtain information regarding the patient's survival status before determining the patient is lost to follow-up.

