8. TRIAL OBJECTIVES

8.1. Primary Objective

- To evaluate the long-term safety and tolerability of ACE-536 in patients with low or intermediate-1 risk MDS who were previously enrolled in study A536-03.

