11.3. Other Safety Assessments

- Physical examination
- Vital signs: weight, heart rate, systolic and diastolic blood pressure
- ECOG Status
- 12-lead ECG
- ADA testing
- The occurrence of a new malignancy or premalignant lesion will be monitored as an event of interest and should be included as part of the assessment of adverse events throughout the course of the study. Investigators are to report the development of any new malignancy or premalignant lesion as a serious adverse event, regardless of causal relationship to study drug, occurring at any time for the duration of the study, from the time of signing the ICF up to and including 3 years of follow-up.

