- Is an important medical event: an important medical event is an event that may not result in death, be life-threatening, or require hospitalization but may be considered an SAE when, based upon appropriate medical judgment, it may jeopardize the patient and may require medical or surgical intervention to prevent one of the outcomes listed in the definitions for SAEs. Examples of such medical events include

allergic bronchospasm requiring intensive treatment in an emergency room or at home, blood dyscrasias or convulsions that do not result in inpatient hospitalization, or the development of drug dependency or drug abuse.

For the purposes of reporting per regulations, any suspected transmission of an infectious agent via a medical product is by default a suspected, unexpected serious adverse reaction (SUSAR) and should be reported in an expedited manner as described in [Section 14.7](#).

Events Not to Be Considered as Serious Adverse Events

Elective hospitalizations to administer or to simplify study treatment or procedures are not considered SAEs.

Adverse Events of Special Interest

Events of new malignancy and premalignant lesions (excluding benign tumors or benign neoplasia) are to be reported as described in [Section 14.7](#) within 24 hours of the investigator's knowledge of the event by fax, or other appropriate method, using the SAE Report Form, and must be considered an "Important Medical Event" even if no other serious criteria apply; these events must also be documented in the appropriate page(s) of the CRF and subject's source documents. Documentation of the diagnosed malignancy must be provided at the time of reporting as a serious adverse event (e.g., any confirmatory histology or cytology results, X-rays, CT scans, etc.).

Malignancies or cancerous tumors are lesions capable of invading into adjacent tissues, and may be capable of spreading to distant tissues. A benign tumor has none of those properties.

Malignancy or cancer is characterized by anaplasia, invasiveness, and metastasis. For MDS studies, these also include progression to high/very high risk of MDS (per IPSS-R²⁶, [Appendix 3](#)), myeloproliferation (e.g., clinically significant increases in blasts), progression to AML, etc.

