### 5.8.6. Adverse Events

All AEs and SAEs occurring after the Study A536-03 (for patients without interruption) or Study A536-05 (for patients with interruption) Cycle 1 Day 1 until approximately 2 months after the last study drug administration (PTFU visit) are to be reported and documented on the AE CRF.

Treatment emergent adverse events (TEAE) are defined as:

- AE starting or worsening from the first date of study drug;
- AE occurs on the first date of study drug and the onset check box is marked “Onset after first dose of study drug”;
- AE with a missing start date and a non-missing stop date on or after the first dose of study drug;
- AE with both a missing start and stop date.

A drug-related TEAE is defined as any TEAE related to the study medication as assessed by the investigator or with missing assessment of the causal relationship.

The following summaries will also be presented:

- Number and percentage of patients reporting each AE, categorized by SOC and PT
- Number and percentage of patients reporting each AE experienced by  $\geq 5\%$  of patients in all patients by PT
- Number and percentage of patients reporting SAE, categorized by SOC and PT
- Number and percentage of patients reporting Grade  $\geq 3$  AE, categorized by SOC and PT
- Number and percentage of patients reporting related AE, categorized by SOC and PT
- Number and percentage of patients reporting AE leading to drug withdrawal, categorized by SOC and PT
- Number and percentage of patients reporting AEs of interest by cycle

Note that counting will be by patient, not event, and patients are only counted once within each SOC or preferred term. If a patient has the same AE at more than one severity, or with more

than one relationship to study drug, the most severe rating or the stronger causal relationship to study drug will be given precedence. Any missing severity, causality, or outcome will not be imputed and classed as unknown.

All AEs will be listed. The following listings will also be provided: 1) patients with SAEs; 2) patients with Grade  $\geq 3$  AEs; 3) patients with AEs leading to discontinuation.; and 4) death.

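### Primary objective is long-term safety, but the 3-year survival, AML and malignancy follow-up is only listed and AE tables are crude percentages: add survival, cumulative-incidence and exposure-adjusted summaries

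*SAP*

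**What the plan says.** Protocol 8.1 gives one primary objective: "To evaluate the long-term safety and tolerability of ACE-536 in patients with low or intermediate-1 risk MDS". The Schedule of Events (footnote 21) sets up "Long-Term Post-Treatment Follow-Up for overall survival (OS), progression to AML, other malignancies/pre-malignancies", which "may be conducted by record review (including public records if allowed by local regulations) and/or telephone contact with the patient". The special-interest row of the same table runs "After signing ICF and until at least 3 years post last dose of IP or until death". Protocol 11.3 makes any new malignancy or premalignant lesion a serious adverse event "from the time of signing the ICF up to and including 3 years of follow-up", and section 14.1 adds that "these events must also be documented in the appropriate page(s) of the CRF". Section 14.1 also places progression to AML, and to high or very high risk MDS, among these events.

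On analysis, SAP 5.8.11 is a single sentence: "A listing of Long-term Follow-up data including the visit date, malignancy status, and survival status will be provided". SAP 5.8.6 reports adverse events as numbers and percentages of patients, each patient counted once per term, with the general collection window closing about 2 months after the last dose (PTFU). Its only time-related table is "Number and percentage of patients reporting AEs of interest by cycle". SAP 5.6 summarises exposure duration but uses it nowhere as a denominator. SAP 5.2 has a general Kaplan-Meier rule for time-to-event variables. The only variables the SAP assigns to that method are durations of transfusion independence and of HI-E response (5.8.2.2 and 5.8.2.5).

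**The concern.** Survival, AML and malignancy are the late outcomes that the 3-year follow-up exists to capture. As planned, the report can show who had an event and some counts. It cannot say how risk accrues over time.

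Two features make crude percentages hard to read here. First, time at risk differs greatly between patients, so a percentage mixes the event rate with the length of observation. Second, death is common in this disease by the protocol's own account (section 7.1), so it competes with AML and malignancy. The secondary response endpoints get time-to-event methods, while the primary safety objective gets none.

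**Working it through.** The documents state no safety rate, event count or sample-size figure on this point, so there is nothing of theirs to reproduce.

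**1. How much follow-up lies outside the general AE window.** Inputs: 36 months of follow-up after the last dose; AE window to about 2 months after it.
- 36 − 2 = 34 months; 34/36 = 94% of post-treatment time.
- Share of planned A536-05 observation: 34/(60 + 36) = 35% for a patient treated 60 months; 34/(12 + 36) = 71% for one treated 12 months.

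**2. Spread of planned AE time at risk.** Inputs: last dose no later than 1825 days from C1D1 (protocol 9.1 and 10.1); 2 months taken as 61 days; AE start at A536-05 C1D1 for interrupted patients and at A536-03 C1D1 for roll-over patients (SAP 4.1 and 5.8.6). For roll-over patients the lead-in assumes a full base-study course: last dose on Day 85 (SAP Appendix 2) plus the 28-day gap is Day 113, which is 112 days after Day 1.

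| Patients | Shortest planned | Longest planned | Ratio |
|---|---|---|---|
| With interruption | 61 days (one dose) | 1825 + 61 = 1886 days | 1886/61 = 31 |
| Roll-over | 61 + 112 = 173 days | 1886 + 112 = 1998 days | 1998/173 = 12 |

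Early death can shorten the lower ends further.

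**3. What that spread does to a percentage.** With an assumed constant rate of 0.10 events per patient-year, the crude percentage is 1 − exp(−0.10 × t): 2.5% at 0.25 years, 9.5% at 1 year, 18% at 2 years and 39% at 5 years. The rate is the same throughout.

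**4. Deaths in the 34 months (2.83 years) after the AE window: illustration.** Assume exponential survival with the medians in protocol 7.1.
- Low risk, 5.7 years: 1 − 2^(−2.83/5.7) = 29%.
- Intermediate-1 risk, 3.5 years: 1 − 2^(−2.83/3.5) = 43%.

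**5. Why AML needs a competing-risk estimate: illustration at 8 years.** Let h be the death hazard, ln 2/median. Set the AML hazard a = h × p/(1 − p), so that a share p of 25% or 30% (protocol 7.1) ever progress before death.
- Cumulative incidence = p × [1 − exp(−(a + h) × 8)]; one minus Kaplan-Meier = 1 − exp(−a × 8).
- Median 5.7, p = 25%: h = 0.1216, a = 0.0405; 18% against 28%.
- Median 3.5, p = 30%: h = 0.198, a = 0.0849; 27% against 49%.
- In the first case, adding withdrawal at an assumed 0.05 to 0.20 per year takes the crude percentage to 16% and 11%, below the 18%. Censoring deaths overstates AML risk, and the crude percentage understates it.

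**6. Time origin for survival.** Entry requires completed A536-03 treatment (protocol 9.2.1). Counting survival from A536-03 C1D1 would therefore give each roll-over patient 112 days, or 112/365.25 = 0.31 years, in which death was impossible by design. A536-05 C1D1 avoids this.

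**The case against.** The strongest reply is that nothing promised is missing. Overall survival and AML are not objectives or endpoints in protocol section 8, and protocol 15.2.2 promises only descriptive safety summaries. The study is single-arm, with no formal sample size and no hypothesis test. All of that stands. A reader might infer that the SAP breaks the protocol; the documents do not support that. The gap is between the objective and the summaries that would make it interpretable, and every proposed addition is itself descriptive.

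A second reply is that a reader might infer late deaths and malignancies appear nowhere but in listings. That goes too far. Death is a reason for study withdrawal (SAP 3.2), and SAP 5.3 tabulates those reasons. A fatal event inside the AE window can enter the SAE and Grade 3 or higher tables under its cause. Malignancies are SAEs for 3 years, and the treatment-emergent definition in SAP 5.8.6 has no end date, so late ones may reach the SAE table. The same section stops AE collection at PTFU, so the SAP leaves this open. None of these counts shows timing or follows a denominator of time at risk.

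Third, the by-cycle table of events of interest does carry time. It is still a percentage, states no at-risk denominator and has no cycles after treatment ends.

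Finally, it may be said that events will be few and late ascertainment incomplete, since it can rest on record review or telephone contact. That is fair. It calls for intervals and a caveat rather than for no estimate.

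**Conclusion.** The point holds as a cheap improvement that should be made. It is not an error that invalidates any planned result. The facts rest on the documents: only a listing for the long-term data, crude percentages for adverse events, exposure never used as a denominator, and Kaplan-Meier specified only for response durations. Outside the general AE window lie 34 of the 36 post-treatment months.

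Three stronger readings should be resisted.
- The 31-fold spread is not general. It fits interrupted patients; for roll-over patients on the SAP's own AE clock it is about 12-fold.
- The 29% to 43% death figure is not evidence about this cohort. It applies general disease medians and an assumed exponential form to selected extension patients, for whom the documents give no survival data. The same limit applies to the AML illustration.
- A reader might infer that progression to high or very high risk MDS should be summarised only to the End of Treatment visit, because IPSS-R needs marrow results and no marrow is scheduled later. Protocol 14.1 makes such progression reportable and the Schedule of Events monitors it for at least 3 years, so a cut-off there would drop reportable events.

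**What to change.** **SAP 5.8.11.** Keep the listing and add, from A536-05 C1D1 for all patients with censoring at last contact:
1. Kaplan-Meier overall survival.
2. Cumulative incidence of AML, and separately of new malignancy other than AML, with death as a competing event.
3. All high or very high risk MDS progression events through follow-up, noting that no marrow is scheduled after the End of Treatment visit, so later ascertainment is incomplete.

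**SAP 5.8.6.**
- Add exposure-adjusted incidence rates with exact 95% confidence intervals beside the AE, SAE and AE-of-interest percentages. Numerator and person-time must start at the same stated origin, which is A536-03 C1D1 for roll-over patients if their A536-03 events are counted.
- If AML or malignancy rates are also given from A536-05 C1D1, count both events and person-time from there and label them so.
- State in one sentence whether malignancy SAEs reported after PTFU enter the SAE table.
- Label any on-treatment versus post-treatment split as descriptive. Under protocol 9.3 and 10.2.1 patients stop for progression, peripheral blasts, persistent WBC increase or another MDS therapy, so the two periods hold differently selected patients.

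**Cost.** SAP wording and a few extra tables and figures, from data the protocol already collects; no new visits or tests. Intervals will be wide if events are few. For example, 5 events in an assumed 300 patient-years give 1.67 per 100 patient-years (exact 95% CI 0.54 to 3.89). The report should also say that ascertainment after PTFU may be less complete.
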